#### 3:

The proportion of participants experiencing successful colonization with *L. crispatus* CTV-05 following dose of study product through final visit (approximately Day 36 and 64) in the LACTIN-V arm.

#### 4:

The proportion of subjects with cervicotypes I-IV compared by study arm.

Primary / Secondary Outcome Safety Measures for Objective 3 (safety and acceptability)

Safety of LACTIN-V and the applicator will be measured by:

The proportion of participants reporting product-related AEs and SAEs through the final visit that are likely related to use of study product compared by study arm, in particular Grade 3 AEs and SAEs.

Acceptability of LACTIN-V and the applicator will be measured by standardized questionnaire about acceptability of the study product and participants' stated willingness to use this type of product in the future, in each study arm.

## 4.0 STUDY DESIGN

This is a Phase 2 randomized double-blind placebo-controlled trial to assess the impact of the live biotherapeutic product LACTIN-V containing *Lactobacillus crispatus* CTV-05 on the vaginal microbiome of young women in South Africa at high risk of HIV acquisition.

The study will also assess the safety of LACTIN-V by comparing the incidence of AEs between women randomized to LACTIN-V or placebo.

We will conduct a randomized, placebo-controlled trial of LACTIN-V in a cohort of young South African women with a non-*Lactobacillus* dominant microbiota, who are sexually experienced, age 18 to 23 years. Enrolment will be continued until 60 women will be randomized into the study.

Eligible women will be treated with oral metronidazole 400 mg twice daily for seven days and will then be randomized 2:1 to LACTIN-V vs. placebo.

Within 8-48 hours of taking the final metronidazole dose, women will receive the study product for five consecutive days, followed by a twice weekly dose for three additional weeks.

After enrolment and metronidazole treatment, women will be followed throughout the 4 weeks of dosing and the 4 weeks of post-dosing phase for a total of 10 weeks (until approximately Day 64).

The primary outcome (**Objective 1**) focuses on the ability of the *L. crispatus* CTV-05 to acutely decrease genital tract inflammation (as a marker of HIV susceptibility). This will be assessed by collecting cervicovaginal fluid and endocervical immune cells at randomization (Day 8), after 4 weeks of treatment with the LACTIN-V vs. placebo (Day 36), and after 4 weeks of post-dosing phase (Day 64).

Direct anti-HIV activity will be assessed with *in vitro* HIV infection assays using vaginal fluid samples from randomization and after treatment: Randomization Visit (Day 8), Follow-up Visit (Day 36), and Final Visit at Day 64.

A secondary outcome (**Objective 2**) is to assess the ability of the *L. crispatus* CTV-05 to establish durable vaginal colonization as with the potential as a self-sustaining prevention strategy. This will be assessed by characterization of the vaginal microbiome at the baseline FRESH Study Visit, and the end of treatment (Day 36) and at the Final Visit (Day 64), after 4 additional weeks during the post-treatment phase.

Finally, while LACTIN-V has been shown to be safe and well tolerated in US women, we will assess the safety and tolerability **(Objective 3)** in this cohort of young South African women up to Week 9 (4 weeks post-dosing phase).

The Umlazi site of the FRESH study enrols approximately 300 women per year into the cohort. During the baseline Screening Visit of the FRESH enrolment process, new cohort members will learn about the parallel LACTIN-V clinical trial, including the findings from the FRESH study which demonstrated the association of a *L. crispatus* cervicotype with a reduced risk of HIV acquisition.

At the **FRESH Study Visit conducted in Week 5** of the FRESH protocol, a vaginal smear is collected sent to the site laboratory for Gram stain evaluation by Nugent score. For STI diagnostics, a vaginal swab for *Neisseria gonorrhoeae, Chlamydia trachomatis, Trichomonas* and *Mycoplasma genitalium* molecular testing will be collected, as well as a urine sample for a Point-of-care (POC) urine testing and a  $\beta$ - hCG-based pregnancy test. Test results for STIs as well as the Gram Stain are expected to arrive within one week.

Any women who enrolled in the FRESH study who express interest in the LACTIN-V trial and during the Week 5 FRESH Study Visit were diagnosed with a Nugent score of 4-10 on vaginal Gram Stain, and without any positive tests for the STIs listed in the exclusion criteria, will be contacted by study staff about their preliminary eligibility for the LACTIN-V trial, and will be offered concurrent enrolment in the LACTIN-V study.

In consideration of their menstrual cycle (they should not be bleeding at the time of enrolment and during the first five days of product administration), a LACTIN-V Enrolment Visit is scheduled at least 7 days out, not to exceed 30 days from the FRESH Week 5 Visit to ensure a high likelihood that the test results of that visit are still relevant.

Women will return to the study clinic for enrolment into the LACTIN-V study. During the informed consent procedure, they will learn details about the LACTIN-V study.

At the **Enrolment Visit 1 (Day 1)**, participants will complete a medical history and undergo a physical examination. Enrolled participants will receive oral Metronidazole 400mg tablets, and are instructed to immediately start the 7-day course (twice daily), to be completed within 8-48 hours of the Randomization Visit on Day 8. A **Check-In Visit 2 (Day 4)** is scheduled to provide additional guidance for the metronidazole administration.

At the **Randomization Visit 3 (Day 8)**, a gynaecological exam will be conducted to collect baseline vaginal microbiome data, including cervical swabs, cervicovaginal lavage fluid and an endocervical cytobrush to assess the microbial composition, cytokines and mucosal HIV target cells. A gram stain and a vaginal swab for *L. crispatus* (including CTV-05) identification will be collected. Only participants who completed their 7-day course of oral Metronidazole will be randomized and receive study product.

The 11 doses of LACTIN-V at 2 x 10^9 cfu/dose or placebo are scheduled to be administered by vaginal applicator for 5 consecutive days and then twice weekly for 3 weeks, throughout Week 1-4 of the study. The first dose of study product is administered as part of the Randomization Visit on Day 8. Participants will be instructed to take the second and third dose on subsequent Days 9 and 10 at home before bedtime. All other doses will remain at the clinic site, where the women are attending regular twice-weekly visits as participants of the FRESH study. During these FRESH visits, they will be handed the remaining LACTIN-V applicators to administer on site according to schedule in a form of directly observed therapy.

During the study, participants will be counselled to use the provided lubricated or unlubricated nonspermicidal condoms during vaginal intercourse. Study staff will provide condoms that have been tested to not interfere with lactobacilli growth. In addition, participants are counselled to avoid vaginal intercourse during the 12 hours before scheduled gynaecological exams, as this activity could lead to microabrasions notable at speculum exam, and could interfere with a correct determination of symptoms related to study product administration. Further, participants will be counselled to avoid sexual intercourse for 12 hours after study product administration to ensure that the product will remain inside the vagina.

**Brief Check-in Follow-up Visits 4 - 10 (Days 11, 15, 18, 22, 25, 29 and 32)** without physical and gynaecological exams to assess adherence, menstrual cycle, sexual activity, condom use, concomitant medications, and AEs, and to administer subsequent doses of study product are scheduled to coincide with regular clinic visits as part of the FRESH schedule (twice weekly either Monday/Thursday or Tuesday/Friday).

Week 1:	Day 8 (where the doses for Day 9 & 10 are handed to participants to take at
	home)
	Day 11 (where the dose for Day 12 is handed to participants to take at home)
Week 2:	Day 15 and 18 (Doses 6 and 7) administered in clinic
Week 3:	Day 22 and 25. (Doses 8 and 9) administered in clinic
Week 4:	Day 29 and 32. (Doses 10 and 11) administered in clinic

At the beginning of Week 5, at the end of the dosing phase, a **Follow-up Visit 11** is scheduled for **Day 36**. This visit will include a physical and gynaecological exam to collect vaginal microbiome data, including cervical swabs, cervicovaginal lavage fluid and an endocervical cytobrush to assess the microbial composition, cytokines and mucosal HIV target cells. A gram stain and a vaginal swab for L. crispatus (including CTV-05) identification will be collected.

Should symptoms or the sexual history suggest the acquisition of an STI, testing for STIs will be included. Acceptability will be assessed using a questionnaire.

During Week 5 – 8, study staff will continue to check in with participants twice weekly for brief **Checkin Follow-up Visits 12 – 18 (Days 39, 43, 46, 50, 53, 57 and 60)** without physical and gynaecological exams to assess menstrual cycle, sexual activity, condom use, concomitant medications, and AEs. These are scheduled to coincide with regular clinic visits as part of the FRESH schedule (twice weekly either Monday/Thursday or Tuesday/Friday).

Week 5:	Day 39
Week 6:	Day 43 and 46
Week 7:	Day 50 and 53
Week 8:	Day 57 and 60

The **Final Visit 19 (Day 64)** 4 weeks post dosing will include a physical and gynaecological exam to collect vaginal microbiome data, including cervical swabs, cervicovaginal lavage fluid and an endocervical cytobrush to assess the microbial composition, cytokines and mucosal HIV target cells. A gram stain and a vaginal swab for L. crispatus (including CTV-05) identification will be collected. Should symptoms or the sexual history suggest the acquisition of an STI, testing for STIs will be included.

Electronic reminders per cell phone will be sent to women prior to each scheduled visit. See complete listing of all study visits in the timeline below:

Wk	Monday	Tuesday	Wednesday	Thursday	Friday	Saturday	Sunday
	(Tuesday)	(Wednesday)	(Thursday)	(Friday)	(Saturday)	(Sunday)	(Monday)
0	Day 1 Enrolment Visit 1 Informed Consent Metronidazole 1 & 2	2 Metronidazole 3 & 4	3 Metronidazole 5 & 6	4 Visit 2 Check-in & dispense Metronidazole	5 Metronidazole 9 & 10	6 Metronidazole 11 & 12	7 Metronidazole 13 & 14
1	8 Randomization Visit 3 Gynaecol. exam	9	10	7 & 8 11 Visit 4 AE Check	12	13	14
2	Dose 1, on site 15 Visit 5 AE Check Dose 6, on site	Dose 2, at home	Dose 3, at home 17	Dose 4, on site 18 Visit 6 AE Check Dose 7, on site	Dose 5, at home 19	20	21
3	22 Visit 7 AE Check Dose 8, on site	23	24	25 Visit 8 AE Check Dose 9, on site	26	27	28
4	29 Visit 9 AE Check Dose 10, on site	30	31	32 Visit 10 AE Check Dose 11, on site	33	34	35
5	36 Visit 11 Gynaecol. exam	37	38	39 Visit 12 AE Check	40	41	42
6	43 Visit 13 AE Check	44	45	46 Visit 14 AE Check	47	48	49
7	50 Visit 15 AE Check	51	52	53 Visit 16 AE Check	54	55	56
8	57 Visit 17 AE Check	58	59	60 Visit 18 AE Check	61	62	63
9	64 Visit 19 Gynaecol. exam						

## 5.0 STUDY ENROLMENT AND WITHDRAWAL

The study plans to enrol non-pregnant women, age 18 to 23 years, diagnosed with a non-*Lactobacillus* dominant microbiota (diagnosed by Nugent 4 - 10).

Enrolment will be continued until 60 women have been randomised into the study. Eligibility criteria for participation in the study are described in detail in sections 5.1 and 5.2.

The consent process will be completed during the Enrolment Visit 1 (Day 1) to determine eligibility. Pregnant women, men and children are excluded from study participation (see section 14.4).

#### 5.1 Subject Inclusion Criteria

Participants must meet all of the inclusion criteria in order to be eligible to participate in the study:

- 1. FRESH study participant.
- 2. Capable of reading and writing English or isiZulu and voluntarily provide written informed consent to participate in the study and comply with all study procedures
- 3. HIV-negative
- 4. Nugent score 4-10 on vaginal Gram stain
- 5. Otherwise healthy women, 18–23 years of age on the day of enrolment
- 6. Regular predictable menstrual cycles or amenorrhoeic for at least 3 months due to use of a long-acting progestin.
- 7. Willing to complete 7-day course of oral metronidazole.
- 8. Willing to be asked questions about personal medical health and sexual history
- 9. Willing to apply study agent vaginally and comply with study examinations
- 10. Willing to self-administer Study Product on dosing days that do not coincide with regular FRESH study visits.
- 11. Agree to try to abstain from sexual intercourse 12 hours prior to study visits that include a gynaecological exam (Randomization Visit 3, Follow-up Visit 11, Final Visit 19).
- 12. Agree to try to abstain from sexual intercourse for 12 hours after study product administration to ensure that the product will remain inside the vagina.
- 13. Agree to abstain from the use of any other vaginal product throughout the trial period from the time of enrolment through the end of the study. Note: Intravaginal products include contraceptive creams such as Gynol II, gels, foams, sponges, lubricants not approved by the study investigators, tampons and douches.
- 14. Must be stable on a reliable method of long-acting birth control and agree to remain on, for the duration of the study (if of childbearing potential) or, of non-childbearing potential (permanently sterile).

#### 5.2 Subject Exclusion Criteria

Participants meeting any of the following criteria when assessed at the Enrolment Visit, will be excluded from the study:

- Urogenital infection (as tested during the FRESH Week 5 Study Visit, reported within 30 days of detection at the LACTIN-V Enrolment Visit).
   Note: Urogenital infection includes urinary tract infection, Trichomonas (T.) vaginalis, Neisseria (N.) gonorrhoeae, Chlamydia (C.) trachomatis, Mycoplasma genitalium.
- 2. Diagnosis of two or more outbreaks of *N. gonorrhoeae*, *C. trachomatis*, *T. vaginalis, Mycoplasma genitalium*, or herpes simplex virus (herpes genitalis) within 6 months prior to enrolment.
- 3. Subject is ineligible if menstrual cycle length is less than 21 days
- 4. Subject is ineligible if deep epithelial disruption is observed on genital examination noted on or before the Randomization Visit
- 5. Positive for HIV (as tested during the FRESH Week 5 Study Visit, within 30 days of the LACTIN-V Enrolment Visit).
- 6. Current pregnancy or within 2 months of last pregnancy
- 7. Vaginal or systemic antibiotic or antifungal therapy within 21 days of enrolment
- 8. Use of disulfiram within past 2 weeks or other contraindication to use of metronidazole
- 9. Any condition requiring regular periodic use of systemic antibiotics during participation in the trial
- 10. Investigational drug use other than LACTIN-V within 30 days or 10 half- lives of the drug, whichever is longer, of Enrolment Visit
- 11. Other planned participation in an investigational drug study while participating in this study
- 12. IUD insertion or removal, pelvic surgery, cervical cryotherapy or cervical laser treatment within the last 2 months prior to enrolment
- 13. Use of vaginal ring (e.g, NuvaRing) within 3 days of enrolment or during the course of the study
- 14. Hysterectomy
- 15. Unwilling to complete 7 days of oral metronidazole (twice daily) with the last dose taken no later than 48 hours prior to randomization (minimum of 12 of 14 doses required)
- 16. Use of new long-acting hormonal treatments. Participant may be enrolled if stable (at least 1 month) on existing therapy as determined by the principal investigator (PI)
- 17. Known allergy to any component of LACTIN-V/placebo or metronidazole or to nitroimidazole derivatives or latex (condoms)
- 18. Any social, medical, or psychiatric condition including history of drug or alcohol abuse that in the opinion of the investigator would make it difficult for the participant to comply with study procedures
- 19. Any serious or chronic illness, deemed incompatible with study participation by the study doctor, including immunosuppression due to cancer chemotherapy, systemic corticosteroids.

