# 6.5 Concomitant Medications/Treatments

The study requires documentation of all medications (name, dose, route, frequency of dosing, and reason for use) taken by participants 30 days prior to enrolment through the final visit (Day 64) or early termination, whichever occurs first.

The following medications are permitted throughout the study:

- Vitamins and other nutritional supplements
- Hormonal contraceptives
- Cough medicine
- Non-steroidal anti-inflammatory drugs
- Prescription and over-the counter medications for allergies and asthma
- Herbal, naturopathic, and traditional preparations (e.g., Chinese traditional medications)
- Externally applied topical medications (except genital area)
- Antibiotics prescribed during the trial, including Metronidazole for BV

The following medications are prohibited throughout the study, and participants will be instructed to not use them throughout the study up to the Final Visit 19 (Day 64):

- Immune suppressants
- Investigational drug preparations other than the study product
- Intravaginal medications/preparations and topical medications/preparations other than the study product applied to the external genitalia

Any other medication/treatment not listed as permitted or prohibited is subject to the judgment of the investigator.

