# 7.0 STUDY SCHEDULE

# 7.1 Enrolment Visit 1

The purpose of the Enrolment Visit 1 is to complete the informed consent process and identify participants who satisfy all eligibility criteria.

Women who are part of the FRESH study cohort can be recruited for the LACTIN-V study. Potentially eligible participants will be approached during the regular Week 5 FRESH Study Visit that includes a pelvic exam and mucosal sampling. Women will receive information about the opportunity to co-enrol in LACTIN-V. Should they be interested in participating in the LACTIN-V study, they will be told that some of the test results routinely collected at the Week 5 FRESH Study Visit will be used to assess their eligibility for LACTIN-V, and that they would be contacted should they meet the following eligibility criteria:

- 1. non-*Lactobacillus* dominated vaginal microbiota as determined by Nugent score 4-10 on vaginal Gram stain
- 2. negative STI testing results
- 3. on stable long acting injectable contraception, either on Depot Medroxyprogesterone Acetate (DepoProvera) or norethisterone enanthate (NetEn), or an IUD or implant for at least 3 months.

Interested women who meet these eligibility criteria for LACTIN-V will be contacted after review of the laboratory results, usually within 7-10 days. In accordance with their menstrual cycle and expected onset of the next menses, they will be invited and scheduled for a LACTIN-V Enrolment Visit that will take place on a date at least 12 days before the next expected menses, and no later than 30 days after the Week 5 FRESH Study Visit.

Eligible women who agree to be enrolled in LACTIN-V will be asked to sign the informed consent form available in English and isiZulu that will describe the purpose of the study, the procedures to be followed, and the risks and benefits of the study, and will include a separate section for consent to store samples for future use. An Assessment of Understanding form, available in English and isiZulu, will be completed to ensure that study participants retained the most important aspects of the provided information. A copy of the consent form will be given to the participant and this fact will be documented in the medical record.

Participants will be asked to provide contact information (i.e., address, email address, home/cell phone number, emergency contact), which will be recorded on the appropriate contact form, which will be kept away from other study forms in a locked cabinet.

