# 7.3 Randomization Visit 3 (Day 8)

Before commencing with the physical and gynaecological exam, eligibility for randomization should be confirmed by reviewing the medical history and all laboratory results.

Only women who had negative STI tests and a Nugent score 4-10 on the vaginal specimen collected at the Week 5 FRESH Study Visit, are enrolled in LACTIN-V and completed a full 7-day course of oral Metronidazole (at least 12 of 14 doses, last dose within 8-48 hours of Randomization Visit 3) will proceed to be randomized. Women who did not complete a full 7-day course of oral Metronidazole and took less than 12 of 14 doses, or took the last dose more than 48 hours before the Randomization Visit 3, will be withdrawn from the study.

Participants will be asked to verify previously reported contact information which will be recorded on the appropriate form.

Additionally, her menstrual cycle history will be re-evaluated to ensure regular menstrual cycles (or amenorrhea with long-acting contraceptives) and that menstruation will not be expected during the next 5 days when the use of the study product for 5 consecutive days (days 1-5) has to occur. If she is not currently having menstrual bleeding and her period is not to be expected within the next 5 days, she will proceed with the Randomization Visit 3.

Participants will undergo the following procedures at the Randomization Visit 3 (Day 8):

- 1. Review of concomitant medications
- 2. The pelvic examination will be conducted in the following order:
  - a. Examination of the external genitalia
  - b. Speculum insertion and examination of vagina, fornices and cervix with naked eye. Water will be used to ease speculum insertion. No lubricant should be used as it could contain chlorhexidine which may kill *Lactobacillus*.
  - c. Vaginal pH
  - d. Vaginal swab for Gram stain (Nugent scoring system)
  - e. Two Vaginal swabs for complete mucosal sampling including identification of vaginal bacteria, lactobacilli species, cytokines and HIV target cells as well as multiomic (e.g. proteomics, metabolomics, etc.) testing
  - f. Cervical (or vaginal) swabs for nucleic acid amplification of N. gonorrhoeae, and C. trachomatis.

- g. A cervicovaginal lavage sample
  h. Vaginal swabs for *L. crispatus* identification with qPCR
  i. Vaginal swab for prostate specific antigen testing as a proxy for recent exposure to semen

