# 11.2 Study Objectives and Outcome Measures

As described in section 3.2 and 3.3, the primary study objectives are to compare LACTIN-V with placebo following a 7-day treatment course with Metronidazole with respect to safety and impact on the vaginal microbiome, specifically *lactobacillus* growth and decrease in pro-inflammatory cytokines and HIV target cells.

In Objective 1, the outcomes of interest will be:

(1) a decrease in genital tract inflammation from baseline (the FRESH Study Visit before enrollment) to Day 36 Follow-Up Visit, as defined by a  $\geq$ 1 Log10 decrease in the concentration of cytokines that have been associated with an increased risk for HIV infection., and

(2) the change in the concentration of cytokines at the Final Visit on Day 64 (4 weeks after dosing phase completed) compared to baseline, number of endocervical CD4+ HIV target cells at Day 36 Follow-Up and Day 64 Final Visits compared to baseline, and in vitro anti-HIV activity of cervicovaginal lavage at Day 36 Follow-Up and Day 64 Final Visits. We will compare each outcome by study arm.

In Objective 2, the outcomes of interest will be:

(1) the presence of *Lactobacillus*-dominant vaginal microbial cervicotypes at the Day 36 Follow-Up Visit, and following the post-dosing phase at the Day 64 Final Visit in the LACTIN-V arm; and

(2) the comparison of *L. crispatus* vs. *L. iners* prevalence between treatment groups, quantity of vaginal *L. crispatus*, presence of the specific CTV-05 *L. crispatus* strain, persistence of colonization after stopping therapy, effect of sex and/or vaginal hygiene practices on colonization by lactobacilli, and stability of vaginal microbial communities over time in the treatment vs. placebo arms.

In Objective 3, the outcomes of interest will be:

- (1) the proportion of treatment related adverse events study arm, in particular Grade 3 AEs; and
- (2) the proportion of participants finding the product acceptable and are willing to use it Page 64 of 124

should it become commercially available, as measured in a standardized acceptability questionnaire.

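### The 21-day antibiotic/antifungal washout is counted from enrolment, so its cover of the Week 5 FRESH specimen that sets eligibility and baseline ranges from 14 days at best to none, depending on the lag

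*Combined protocol and SAP*

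**What the plan says.** Section 5.2 opens by excluding "Participants meeting any of the following criteria when assessed at the Enrolment Visit", and criterion 7 in that list is "Vaginal or systemic antibiotic or antifungal therapy within 21 days of enrolment". It does not mention the Week 5 FRESH visit, although criteria 1 (urogenital infection) and 5 (HIV) in the same list are tied to that visit.

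Section 4.0 has the LACTIN-V Enrolment Visit "scheduled at least 7 days out, not to exceed 30 days from the FRESH Week 5 Visit". Section 7.1 repeats the upper limit: "no later than 30 days after the Week 5 FRESH Study Visit".

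The Week 5 specimen then does two jobs:

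- **Eligibility.** Section 7.3 lets through to randomization "Only women who had negative STI tests and a Nugent score 4-10 on the vaginal specimen collected at the Week 5 FRESH Study Visit", subject to the metronidazole requirement. Neither section 7.1 nor Appendix A has a pelvic examination or Gram stain at Enrolment Visit 1. The next Gram stain is on Day 8, after metronidazole.
- **Baseline.** Section 11.2 defines the first Objective 1 outcome as "a decrease in genital tract inflammation from baseline (the FRESH Study Visit before enrollment) to Day 36 Follow-Up Visit". Section 3.4.1 names both the FRESH visit and Day 8 as comparators, and section 4.0 collects Objective 1 samples at Day 8.

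Section 6.5 has medications recorded from 30 days before enrolment. That is a record, not an exclusion.

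**The concern.** A washout before a microbiological eligibility test is there so that the test reflects the woman's usual flora. Here the test is done at Week 5, but the washout is counted from a later date that varies between women. Every woman starts metronidazole on the day of enrolment, so antibiotic-free days just before enrolment matter mainly for what they imply about the earlier specimen, and they imply less as the lag grows.

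The plan itself cares whether the Week 5 results still hold at enrolment: section 4.0 caps the gap at "30 days from the FRESH Week 5 Visit to ensure a high likelihood that the test results of that visit are still relevant". Criterion 7 does not serve that aim fully.

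Two things are at stake. A Nugent score may be read shortly after therapy, or be followed by therapy before enrolment. And the cytokine baseline may be unrepresentative: a baseline already lowered by recent therapy makes a fall of 1 log10 or more harder to reach, while an extra off-study course after the specimen could make a fall more likely. Either can move a woman across the responder line where the FRESH visit is the baseline.

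**Working it through.** The plan gives no figure for how much of the period around the specimen the washout covers, so there is none to reproduce. The sample-size calculation is not involved. For the record, its power of more than 88% (10% vs 50%, 20 vs 40 women, two-sided Fisher's exact test at 5%) is reproduced by exact enumeration at 0.891.

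**Inputs.** Washout of 21 days back from enrolment (section 5.2, criterion 7). Lag d from Week 5 to enrolment of 7 to 30 days (sections 4.0 and 7.1), which is 24 possible whole-day lags. Look-back of 30 days before enrolment (section 6.5). Results after about one week (section 4.0).

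**Convention.** The specimen day is day 0 and enrolment is day d. A woman whose last therapy was on day t passes criterion 7 if d − t > 21. If exactly 21 days counts as outside the washout, every limit moves by one day.

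**Step 1: cover of the specimen.** The washout starts on day d − 21. Clear days guaranteed before the specimen = max(0, 21 − d). Latest therapy day allowed = d − 22.

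| d | Washout starts on day | Clear days before specimen | Latest therapy day allowed |
|---|---|---|---|
| 7 | −14 | 14 | −15 |
| 14 | −7 | 7 | −8 |
| 20 | −1 | 1 | −2 |
| 21 | 0 | 0 | −1 |
| 22 | +1 | 0 | 0 |
| 30 | +9 | 0 | +8 |

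No permitted lag gives the specimen 21 clear days. For d = 7 to 20 the washout includes day −1, day 0 and every later day up to enrolment.

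**Step 2: who passes.**

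| Last day of therapy | Lags at which she passes | Count of 24 |
|---|---|---|
| −7 | 15 to 30 | 16 |
| −1 | 21 to 30 | 10 |
| 0 | 22 to 30 | 9 |
| +1 (single dose) | 23 to 30 | 8 |
| +7 (7-day course, days 1 to 7) | 29 to 30 | 2 |

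These are counts of lags, not of women; the documents do not give the distribution of lags.

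**Step 3: therapy prompted by Week 5 results.** With results at about day 7, a 7-day course on days 7 to 13 would need d > 13 + 21, that is d ≥ 35. The limit is 30, so she cannot pass.

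**Step 4: what the look-back captures.** It starts on day d − 30. The interval from Week 5 to enrolment is therefore recorded at every permitted lag. Before the specimen it reaches 30 − d days: 23 at d = 7, 9 at d = 21 and 0 at d = 30. A window opening 21 days before Week 5 begins 21 + d days before enrolment: 28 at d = 7, 29 at d = 8, 30 at d = 9 and 51 at d = 30. The current look-back covers it only for d ≤ 9.

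**Step 5: weight of one woman.** One reclassified responder moves the placebo rate by 1/20 = 5 percentage points and the LACTIN-V rate by 1/40 = 2.5 points.

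**The case against.** The strongest reply is that the gap is narrow and its effect small. Much of that stands.

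- A reader might infer that any woman treated just before or after the specimen still qualifies. She does not at d = 7 to 20, where therapy the day before, on or after the specimen already excludes her.
- A reader might expect treatment triggered by the Week 5 results to be the main route, since section 2.6.2.2 speaks of referral for treatment. A urinary tract infection or listed STI found at Week 5 already excludes under criterion 1, and a 7-day course begun when results arrive cannot pass within 30 days (step 3). For BV, the same section provides study-supplied metronidazole, which is given at enrolment.
- A reader might say the gap admits women outside the target population. A woman who still scores Nugent 4 to 10 after earlier therapy meets the definition in sections 5.0 and 5.1.
- Eligibility is settled before randomization, and every woman takes metronidazole between Week 5 and Day 8, so no arm should gain. Therapy after the specimen is at least recorded.
- No document says that the specimen needs a full 21-day washout.

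What remains is incidental therapy before or on the specimen day: one STI treated earlier (criterion 2 requires two or more outbreaks in six months), candidiasis, or a non-genital infection. No other criterion covers these. Long lags are also foreseeable: women are usually contacted at 7 to 10 days, and enrolment must then fall at least 12 days before expected menses, on a Monday or Tuesday.

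**Conclusion.** The point holds as a lag-dependent gap. The washout is tied to enrolment, while the specimen that fixes eligibility and the section 11.2 baseline is 7 to 30 days older. Protection before the specimen falls from 14 days to none, and from d = 22 therapy on the specimen day or shortly after it, up to day 8 at most, is also allowed.

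The consequence is non-differential noise in the baseline and in the responder classification. Its size cannot be computed, because the documents give neither the distribution of lags nor the frequency of such therapy. They do not support reading it as bias in favour of an arm. The noise reaches the responder outcome only where the FRESH visit is the baseline, as section 11.2 has it. Nor can it always be examined afterwards: at the longest lag, therapy that ended before the specimen is not recorded at all. The limits assume that exactly 21 days falls inside the washout.

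**What to change.** Reword criterion 7 to exclude vaginal or systemic antibiotic or antifungal therapy from 21 days before the Week 5 FRESH specimen through enrolment. If a full 21 days before the specimen is judged more than is needed, the minimum is to keep the existing 21 days before enrolment and add any such therapy between the specimen and enrolment. That closes the gap after the specimen but not the one before it.

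Set the section 6.5 look-back to the earlier of 30 days before enrolment or 21 days before the Week 5 visit. Counting from the Week 5 visit alone would shorten the present 30 days at lags of 7 and 8 days.

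The cost is one reworded criterion and one reworded look-back. Sample size and power calculations do not change. A few recently treated women become ineligible, from a cohort that enrols about 300 a year.
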